2 BACKGROUND AND RATIONALE

2.1 Background on Condition, Disease, or Other Primary Study Focus

Within organ transplant, despite dramatic improvements in acute rejection rates, long-term graft survival has not improved to nearly the same degree. In kidney transplant, since 2003, there has been a 50% reduction in acute rejection rates; yet, during this same period of time, the allograft half-life has only increased by a modest 0.6 years.^{6,7} The most recent report from the Scientific Registry of Transplant Recipients (SRTR) demonstrates a historically low one-year acute rejection rate of 10%, with a suboptimal five-year graft survival rate of 70%.⁴ Drug-related problems, which encompass medication errors, non-adherence and adverse drug events, are a predominant cause of deleterious clinical outcomes in kidney transplant recipients; most notably, graft loss.²² Our previous research, as well as studies from other groups, has demonstrated that approximately two-thirds of transplant recipients will experience at least one medication error.¹¹⁻¹³ Of more concern, nearly one in eight kidney transplant recipients experience a medication error which directly contributes to hospitalization and doubles the risk of graft loss. These medication errors are usually the result of unintentional non-adherence: patients have difficulty obtaining medications, gets confused from the fragmented care they receive or forget to take medications in a timely manner.¹⁴ Non-adherence has now been recognized as a major contributor to late acute antibody mediated rejection (AMR), the development of donor specific antibodies (DSA) and subsequent graft loss. In a landmark study by Sellares et al, 315 kidney transplant recipients were followed for roughly three years post-transplant; 47% of the 50 allografts that failed during this time were due to AMR; 32% of patients were identified as non-adherent and one-half of all AMRs were due to this. Remarkably, medication non-adherence was 10 times more frequent in patients with graft failure (32% vs. 3%, $p<0.001$).²² As most medication non-adherence is unintentional, with the proper monitoring and follow-up, this devastating risk factor is modifiable. Other drug-related problems, beyond non-adherence, also significantly contribute to deleterious post-transplant events. A study by Friedman et al demonstrated that of 149 medication errors identified in 93 ambulatory organ transplant recipients, 44% were due to iatrogenic causes, including 13% from a prescribing error and 13% from a dispensing error. Importantly, 26% of these errors led to clinical significant events, including

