Also of concern with the use of chronic immunosuppression therapy in the ambulatory care setting are drug interactions. The calcineurin inhibitors and mTOR inhibitors, which are widely utilized immunosuppressants, are metabolized through the cytochrome P450 3A4/5 enzyme system, making them prone to interactions. Due to their effects on the renal and nervous system, these drugs are also frequently associated with pharmacodynamic drug interactions and drug-disease interactions. This includes interactions with classes of medications that are the most frequently prescribed in the outpatient setting, such as NSAIDs and ACE inhibitors. These interactions can result in an acute and dramatic reduction in renal function and electrolyte disturbances, particularly hyperkalemia.^{32,33} The impact of drug-related problems leading to graft loss on clinical and economic outcomes cannot be overstated. Annual death rates are more than three times higher in those with kidney allograft failure (9.4%), as compared to those with a functioning transplant (2.8%).³⁴ A well-functioning kidney transplant has also been shown to dramatically reduce the progression of cardiovascular disease and associated events.³⁵⁻³⁷ In other organ types, graft loss universally leads to either retransplant or death. In terms of cost, transplantation is highly cost-effective. However, due to high and varied peri-operative costs associated with this surgery, the break-even point can range from two to 11 years after transplant.^{38,39} Once a kidney transplant fails, patients return to dialysis and costs to provide care accrue at a significantly higher rate.^{40,41} Our research indicates that kidney transplant recipients that experience clinically significant medication errors spend five more days in the hospital for readmissions, costing more than \$18,000 per case.¹⁴ These data, taken in its entirety, establishes the need for innovative interventions designed to improve medication safety and reduce drug-related problems in transplant recipients, by decreasing medication errors, non-adherence and adverse drug events;¹⁰ Such medication safety improvements are needed to demonstrate significant progression in

the optimization of long-term graft outcomes and patient survival.

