9.3.2 Secondary outcomes

Secondary assessment will include a cost benefit analysis. Overall health care costs accrued during the 24-month study, as well as those accrued in the 24-months prior to study initiation will be analyzed and compared between the control and intervention groups. Cost data will be standardized using the VA Health Economics Resource Center (HERC) definitions, which normalizes regional differences in costs due to variation in cost of living indices. As with the primary outcome, we will also acquire and link CMS claims data to gain a comprehensive assessment of costs, including those that accrue from non-VA care (after study completion). Costs will also be sub-analyzed into three predominant categories: inpatient costs, outpatient costs and pharmacy costs, as described in the statistical analysis plan. To fully assess if the intervention is has a direct monetary benefit, we will measure costs of the intervention will include estimates of time and resources to implement the dashboard and train and support the intervention site pharmacists. Similar to primary outcome, we expect that as ER visits and hospitalizations decrease within the intervention arm, there will be a corresponding decrease in overall costs as well, predominantly driven by inpatient costs. We expect this decrease to occur during the second 12 months of the study period, as the intervention is likely to have a lag effect on this outcome as well.

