9.4 Data Analyses

The data analysis will incorporate the intent-to-treat principle; namely, all participants enrolled in the intervention group will be included in the analysis and compared to all of the patients captured within the control group. If a patient dies, has graft loss or moves out of their study site, their data will be censored at that time point. For comparative statistical assessments within the utilization outcomes, the two groups will be compared using a generalized linear mixed models (GLMM) approach.⁵⁴ This approach allows for measurement of participants at different time points, clustering by study site, missing data under the assumption of missing at random (MAR), time varying or invariant covariates, and can also account for the effect of correlated longitudinal measurements within participants. In addition, GLMM accommodates a wide range of distributional assumptions such as dichotomous (e.g. binomial), count (e.g. Poisson), continuous

(e.g. Gaussian), and categorical or ordinal outcomes. For comparing the primary outcome (ED visit and hospitalization rates), we will use GLMM (with appropriate link function) with counts of these events as the outcome variable and intervention group (yes/no) as the primary independent variable. This analysis is equivalent to Poisson regression or negative binomial regression (in the case of over-dispersion), both special cases of GLMM. Additional adjustment covariables will be added to the model in a second set of analyses. Covariates will include patient sociodemographics: age, sex, race, comorbidities (using modified Elixhauser definitions), marital status and education. In these models, donor information (age, sex, race, deceased or living) and transplant characteristics (HLA mismatches, ischemic times, panel reactive antibody levels, time since transplant) will also be included. This will assist in making valid intervention effect estimates after accounting for baseline differences, as there may be patient-level differences between groups. The magnitude of between intervention differences on outcome variables (effect sizes) at each time point will be estimated using appropriate contrasts in the corresponding GLMM models.

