calibration (PSC).⁵⁷ We will assess the effect of the intervention on different sources of cost which include inpatient, outpatient and pharmacy in addition to the total aggregated cost. The cost models will be estimated using log-normal or gamma models (special cases of GLMM) to examine the association of the intervention with cost, adjusting for the aforementioned patient sociodemographics, donor information and transplant characteristics. Cost will be obtained from VINCI CDW and HERC as inpatient, outpatient, pharmacy and total aggregate for two years prior to the study period and for the two years of the intervention. We will also account for non-VA costs through linkage with CMS claims data. We will estimate different models adjusting for the clinical outcomes in order to examine the robustness of the results. GLMM allows for correlation between cost categories as well as for the likely skewed distribution of cost data. The Park test will be performed to check for the appropriate distribution of the cost data and AIC and BIC statistics for goodness of fit. Since, inpatient cost could exhibit a point mass of zero, we will use marginalized two-part models that are appropriate for semi-continuous data to model the relationship between the intervention and inpatient cost.^{58, 59} In general, statistical analyses will use two-sided tests with alpha set at 0.05.

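### Section 9.4 censors every patient's data at graft loss or a move, so the planned 24-month total cost is truncated; cost should be exempted, though the likely distortion between arms is small.

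*Combined protocol and SAP*

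**What the plan says.** Section 9.4 opens with the intent-to-treat principle and then gives one general rule: "If a patient dies, has graft loss or moves out of their study site, their data will be censored at that time point". The rule precedes the utilization models, is not limited to them and makes no exception for cost.

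The synopsis lists 24-month total cost by arm as a secondary objective. Section 9.3.2 describes the outcome as "Overall health care costs accrued during the 24-month study", analysed together with the 24 months before the study, and adds: "Secondary assessment will include a cost benefit analysis". The cost paragraph of Section 9.4 obtains cost as "total aggregate for two years prior to the study period and for the two years of the intervention". It names no exposure term and no analysis that continues past graft loss or a move. Its robustness models adjust for clinical outcomes. The missing-data paragraph offers multiple imputation and maximum likelihood.

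On timing, Section 9.3.2 says of the cost reduction: "We expect this decrease to occur during the second 12 months of the study period".

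**The concern.** A sum that stops at graft loss is not a 24-month total. Graft loss also occurs after randomization and lies on a pathway that the protocol itself describes. Section 2.1 says drug-related problems "are a predominant cause of deleterious clinical outcomes in kidney transplant recipients; most notably, graft loss", and, on cost, "Once a kidney transplant fails, patients return to dialysis and costs to provide care accrue at a significantly higher rate". Stopping the count there removes by rule the cost that a prevented graft loss would save afterwards.

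Nothing else planned restores it. Adjusting for clinical outcomes does not add back excluded cost, and imputation and likelihood methods deal with data that are missing, not data set aside.

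Two patterns could follow. If cost is analysed per unit of observed time, a saving that comes only from fewer graft losses shows as no effect. If truncated totals are compared without exposure handling, the arm that keeps its grafts longer accumulates more counted time and can look slightly more expensive. The plan does not say which approach applies.

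**Working it through.** **The plan's own figures.** No cost effect or cost sample size is stated, so there is none to reproduce. The utilization sample size does reproduce. With 1.269 × 2 = 2.538 ED visits per person over 24 months and a ratio of 0.75, n per arm = (1.960 + 0.842)² × (1/2.538 + 1/1.9035) / (ln 0.75)² = 87.2. The design effect is 1 + 134 × 0.05 = 7.7, and 2 × 87.2 × 7.7 = 1,343 against the stated 1,350. The question here is what the cost analysis estimates, not an error in a stated number.

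**Inputs from Section 2.1.** Kidney graft survival is 70% at five years. Annual death is 2.8% with a functioning graft and 9.4% after failure.

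**Assumptions.**
- Full 24-month follow-up, with the kidney five-year figure applied to all recipients.
- Kidney share s of 0.5 to 1 (the documents give none).
- No post-loss time for other organs, because Section 2.1 says: "In other organ types, graft loss universally leads to either retransplant or death". Retransplanted patients would add some back.
- Cost rate after loss k = 2 to 3 times the rate before it.
- A 25% cut in graft loss. Section 9.2 uses 25% for encounters, not for graft loss.

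**Model.** Three states: functioning, graft lost, dead. The graft-loss hazard g is −ln(0.70)/5 = 0.0713 per year, or 0.0713 − 0.028 = 0.0433 if the 70% counts deaths as failures. With a = g + 0.028, per kidney patient over two years:
- functioning time F = (1 − e^(−2a))/a = 1.864 (g = 0.0433) or 1.814 (g = 0.0713) years
- post-loss time L = g/(a − 0.094) × [(1 − e^(−0.188))/0.094 − F] = 0.078 or 0.126 years
- cumulative graft loss 8.1% or 12.9%

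With the functioning-graft cost rate set to 1, full cost per patient is F + ksL, person-time is F + sL, and the share of cost dropped is ksL/(F + ksL).

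**Worked cell (g = 0.0713, s = 1, k = 3).** Full cost is 1.814 + 3 × 0.1255 = 2.190, and 0.3765/2.190 = 17.2% is dropped. With 0.75g from day 1, F = 1.8455 and L = 0.0953, so full cost is 2.131. Per person-year: (2.131/1.941) / (2.190/1.939) = 0.972.

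**Range (cost ratios, intervention to control).**

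| Cell | Cost dropped | Effect starts | Full, per person-year | Full, per patient | Censored, per person-year | Truncated total |
|---|---|---|---|---|---|---|
| g 0.0433, s 0.5, k 2 | 4.0% | day 1 | 0.995 | 1.000 | 1.00 | 1.011 |
| same | 4.0% | month 13 | 0.999 | 1.000 | 1.00 | 1.003 |
| g 0.0713, s 1, k 3 | 17.2% | day 1 | 0.972 | 0.973 | 1.00 | 1.017 |
| same | 17.2% | month 13 | 0.993 | 0.993 | 1.00 | 1.004 |

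Across all combinations, the full per-patient ratio is 0.973-1.001 with an effect from day 1 and 0.993-1.000 from month 13.

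**Primary rate.** Assume encounters are 1.5 to 3 times as frequent after loss. A pre-loss ratio of 0.75 becomes 0.758-0.793 with full follow-up if there is no effect after loss. It becomes 0.729-0.748 if the effect persists and graft loss also falls 25%. The shift is modest and its direction is not fixed.

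**Moves.** No rate is given. If all of the 15% loss to follow-up in Section 9.2 were moves at a constant rate, h = −ln(0.85)/2 = 0.0813 per year and 1 − (0.15/0.0813)/2 = 7.7% of person-time would go. No difference by arm can be derived.

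**The case against.** The strongest counter-argument is that the expected saving survives the rule. Section 9.3.2 expects cost to fall because ER visits and hospitalizations fall, mainly through inpatient cost. That saving arises on functioning grafts and is counted, as is an admission leading up to graft loss. Section 9.3.2 also calls graft survival exploratory and unpowered, and it is still compared by arm. This stands. A reader might infer that the analysis omits every saving from preventing graft loss or cannot address monetary benefit; the documents support only that cost after the loss is left out.

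Timing is a second objection. About three-quarters of post-loss time falls in months 13-24, so a reader might think the omission is concentrated where the effect is expected. But about two-thirds of that later post-loss time follows grafts lost in months 1-12, before the expected effect. This also stands, and it is why the month-13 ratios lie so close to 1.00.

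Third, the two-year cost window in Section 9.4 could be read as full follow-up. It describes what data are obtained and does not override the censoring sentence. If full follow-up was meant, the two statements still need reconciling.

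Fourth, follow-up on a functioning graft at the assigned site is a coherent target, and Section 4.2 already allows rolling entry and exit. That is fair for the encounter rate. It does not turn a truncated sum into the stated 24-month total, and Section 4.2 gives no method.

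**Conclusion.** The inconsistency is real: under the stated rule the cost analysis does not estimate the outcome that the synopsis and Section 9.3.2 define, and no planned analysis fills the gap. The practical effect is small. The 4-17% is a share of total cost left out, not a bias between arms. Per person-year, the gap between full and censored ratios is 0.5-2.8% with an effect from day 1 and 0.1-0.7% from month 13. With the later start, truncated totals and full per-patient totals each stay within 1% of 1.00, although in the most extreme cell they sit on opposite sides of it (1.004 against 0.993).

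These sizes depend on the assumed cost multiplier, kidney share and 25% cut in graft loss, and on a kidney registry figure applied to all recipients. They illustrate scale and do not estimate it.

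A reader might also infer that the primary encounter rate is biased, or that moves bias the comparison. Neither follows. With person-time exposure, the censored rate is valid for time on a functioning graft at the site, and the documents give no basis for different move rates by arm. Severity: minor.

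**What to change.** In Section 9.4, exempt cost from censoring at graft loss and on moving site. Count each patient's cost under the site of origin from entry to death or month 24, state how unequal exposure is handled, and report the graft-loss- and move-censored cost as a sensitivity analysis. Align the cost wording of Sections 9.3.2 and 9.4 with the censoring sentence.

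For encounters, keep the planned censored rate, name the person-time offset, and report the full-follow-up rate beside it as a sensitivity analysis.

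The change is wording only and uses the CDW, CMS and SRTR linkages already planned in Section 10.1. It has three downsides. Post-loss and post-move time is less influenced by the pharmacist and dilutes the contrast somewhat. Non-VA care is captured incompletely for patients without Medicare, which Section 9.3.1 says most, not all, have. Capturing VA care at another site after a move assumes that the research CDW extract covers that site.

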4.3 Study Enrollment Procedures

Once IRB approval is obtained (via central IRB), each potential participating pharmacist will undergo informed written consent. Following this, each site will be randomized to

standard care or standard care plus the pharmacist-led intervention. To ensure a roughly equal number of patients between the two comparison groups, randomization will be stratified by estimates veteran organ transplant recipients (<125 versus ≥ 125 active patients). After randomization, each participating pharmacist will be informed of their assigned group. Those in the intervention arm will be trained on the dashboard system, utilizing the dashboard, and delivering the intervention. Those in the usual care group will continue to provide the same level of care they are currently providing as part of their normal day-to-day activities and job functions.

If a site or participating pharmacist withdraws prior to study initiation, if possible, it will be replaced with a suitable alternative site/pharmacist. If a site pharmacist withdraws after initiation, the investigational team will determine if the site needs to be replaced. This will depend on how far along the intervention is and the number of veterans impacted by the withdrawal.

Because this is a cluster-randomized trial, and randomization occurs at the site level, we will not recruit, consent, or enroll at the subject level. We will request waiver of written documentation of patient informed consent. We request waiver of HIPAA for all patients.

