9.2.1 Treatment Assignment Procedures

Randomization will occur at the site level (cluster randomized trial). Ten sites will be randomized to either the intervention arm or usual care arm using statistical software (SAS, SAS Institute, Cary, NC). Randomized will occur after all sites have agreed to participate and site-level regulatory approval has occurred. Randomization will be stratified by site using estimated sample size (<125 vs. ≥ 125 veteran organ transplant recipients). This will be done to ensure an approximate even distribution of patients across study arms.

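### Sites are randomised within two size strata, but no section 9.4 model includes the stratum; with ten sites this costs power if site size explains more than about 5–10% of the variance in site rates

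*Combined protocol and SAP*

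**What the plan says.** Section 9.2.1 states: "Randomization will be stratified by site using estimated sample size (<125 vs. ≥ 125 veteran organ transplant recipients". Section 4.3 gives the same cut-point: "randomization will be stratified by estimates veteran organ transplant recipients (<125 versus ≥ 125 active patients". The reason given in 9.2.1 is patient numbers: "This will be done to ensure an approximate even distribution of patients across study arms".

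Section 9.4 sets out the primary analysis as a GLMM "with counts of these events as the outcome variable and intervention group (yes/no) as the primary independent variable", with clustering by study site accounted for. A second set of models adds covariates: "Covariates will include patient sociodemographics: age, sex, race, comorbidities (using modified Elixhauser definitions), marital status and education". Donor variables follow, and "transplant characteristics (HLA mismatches, ischemic times, panel reactive antibody levels, time since transplant) will also be included". The cost models reuse that list. Neither the stratum nor site size appears in any of them.

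One statement points the other way. The synopsis (Design and Outcomes) says the efficacy comparison will adjust for patient, provider and facility characteristics. Section 9.4 names no provider or facility variable.

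**The concern.** Stratified allocation makes the two arms share, fully or nearly so, any difference in encounter rates between large and small sites. The true sampling variance of the arm contrast is then smaller than under simple randomisation. A model without the stratum does not use this: it leaves the large-versus-small difference in the between-site variance, so the standard error is too large for the design that was run.

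With five sites per arm, between-site variance largely decides the width of the confidence interval, and there is little precision to give away. The synopsis adds a second difficulty. It commits to facility adjustment without naming a variable, so the choice of facility covariates stays open until after outcomes are available.

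**Working it through.** **Inputs from section 9.2.** Ten sites, five per arm; 1.269 ED visits per person-year; 24 months of follow-up; 25% relative reduction; ICC 0.05; two-sided alpha 0.05; 80% power; N = 1,350, or 1,600 after 15% loss.

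**Reproducing the plan's figure.** Expected counts per patient are 1.269 × 2 = 2.538 and 0.75 × 2.538 = 1.9035. Unclustered n per arm = (1.960 + 0.8416)² × (2.538 + 1.9035) / (2.538 − 1.9035)² = 7.849 × 4.4415 / 0.4026 = 86.6. The design effect with 135 patients per site is 1 + 134 × 0.05 = 7.7. The total is 2 × 86.6 × 7.7 = 1,334, close to 1,350. Dividing 1,350 by 0.85 gives 1,589, close to 1,600.

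**Implied variance of a site log-rate.** 80% power at ln(0.75) = −0.2877 implies Var(log RR) = (0.2877 / 2.8016)² = 0.0105. With five sites per arm, Var(log RR) = 2σ²/5, so σ² = 0.0105 × 5/2 = 0.026. This is the total variance of a site log-rate, including sampling noise within the site. Below, R² is the share of that total explained by the stratum.

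**Assumptions not in the documents.** R² (range 0 to 0.40), the number of sites per stratum (4 and 6 in the main case), and a t test on site log-rates as a stand-in for the GLMM with small-sample inference: 8 df without the stratum, 7 with it.

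**Simulated results, 4/6 split, t reference**

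| R² | Power without stratum | Power with stratum | Type I error without stratum |
|---|---|---|---|
| 0 | 69% | 67% | 5% |
| 0.10 | 69% | 72% | 4% |
| 0.20 | 69% | 77% | 3% |
| 0.40 | 68% | 87–88% | 1% |

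Type I error with the stratum stays at about 5%. The first row agrees with the non-central t distribution at non-centrality 0.2877 / √0.0105 ≈ 2.80: 69% with 8 df and 67% with 7 df. With the stratum in the model, non-centrality rises to 2.80/√(1 − R²), for example 3.13 at R² = 0.20. Without it, the true variance falls in the same way but the estimated standard error does not, so power stays flat and the test becomes conservative.

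**Second check.** A separate simulation built from N = 1,350 and ICC 0.05, with R² taken as the share of between-site variance, runs a few points higher but shows the same pattern. Without and with the stratum: 73.1% and 71.3% at R² = 0; 73.3% and 73.3% at 0.05; 73.1% and 75.2% at 0.10; 73.3% and 79.2% at 0.20. Break-even is about 0.05. With a 5/5 split, which cannot be divided evenly between arms, it is nearer 0.10 (72.8% and 73.3%), and the cost at R² = 0 is larger (73.3% and 69.6%).

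**Dependence on the reference distribution.** Section 9.4 states no df method. With a large-sample Wald z test and maximum-likelihood variance (4/6 split), type I error without and with the stratum is about 12% and 15% at R² = 0, and 7.8% and 14.4% at R² = 0.20.

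**The case against.** The strongest case against is that the stratification was adopted to balance patient numbers, not to control a prognostic factor, and that nothing in the documents links site size to encounter rates. If there is no link, the term costs a degree of freedom and returns nothing. This stands as a limit on size: the gain is conditional. It does not remove the point, because restricted allocation has the same effect on the contrast whatever its motive, and the loss at R² = 0 is small beside the possible gain.

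Three stronger readings are tempting, and the documents do not support them.

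- A reader might infer that power is lost whenever site size is related to encounter rates. With eight between-site degrees of freedom, a weak relation (below about 5–10% of variance) does not repay the one spent.
- A reader might infer that the analysis ignores the cluster design. It does not: section 9.4 models clustering by site.
- A reader might infer that the planned test necessarily runs below 5%. That holds only with a small-sample reference distribution, which section 9.4 neither specifies nor excludes. Under Wald z inference the test without the stratum can exceed 5%, and adding the stratum alone makes that worse.

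The synopsis's promise of facility adjustment might be read as covering the stratum, since site size is a facility characteristic. It names no variable and section 9.4 does not carry it through, so it leaves a conflict to reconcile and does not close the gap.

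**Conclusion.** The point holds in a conditional form. The randomisation stratum is missing from every model in section 9.4, and the synopsis and section 9.4 disagree on facility adjustment. Under t-based inference and a 4/6 split, adding the stratum gains about 3 points of power at R² = 0.10, 8 at 0.20 and 19 to 20 at 0.40. It loses about 2 points at R² = 0, and between 3 and 4 with a 5/5 split. Under that inference the omission is conservative, so it threatens precision and not the false-positive rate. R² and the split are assumptions, so no single figure can be given for this trial. The change is worth making because the possible gain is much larger than the possible loss, provided the degrees of freedom are handled properly.

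**What to change.** In section 9.4, add the randomisation stratum (<125 or ≥125, as classified at randomisation) as a fixed effect in the primary GLMM and in the adjusted and cost models. In the same sentence name a small-sample degrees-of-freedom method, for example Kenward-Roger or between-within, and say how it applies to whichever count model is selected. The two must go together, because the term alone would raise type I error under large-sample Wald inference.

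Reconcile the synopsis with section 9.4: either list the provider and facility covariates intended, with the stratum among them, or remove the promise. Graft and patient survival, which section 9.3.2 treats as exploratory and unpowered, need not be part of this change.

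The cost is a short addition to the text and one between-site degree of freedom (8 to 7). No new data are needed and N does not change. The revision should be fixed before outcome data are compared by arm.
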